At the end of the 90 day treatment phase of Part 1, a pre-specified interim analysis will be performed to evaluate the initial response to therapy and validate the plan for the overall number of patients and dose cohorts. Predefined rules will be used to adapt the protocol. The trial may either be stopped for futility, or continued with some design adaptations for the treatment phase in Part 2. Allowable pre-specified adaptations include calculation of the sample size for Part 2 (ranging from 48 - 100 patients) and addition of a dose arm (either 25 mg or 100 mg b.i.d) according to pre-defined criteria, as described in the interim analysis section (Section 3.5). As a result of available data from interim analysis Part 1 (IA1) of the trial, part 2 of the study will recruit approximately 50 randomized patients. Based on IA1 results, an additional 100 mg dose was chosen by the DMC to be added into Part 2. No further adaptations of the study are planned. Treatment arms in Part 2 will include placebo and four doses of LNP023 given twice daily.

For both parts, each patient will participate in a run-in period, during which a full physical examination, medical history, concomitant medication vital signs, ECG evaluation, vaccination, BP control assessment, repeated 24h-UP, eGFR assessment, safety laboratory tests [REDACTED] will be performed.

If not previously vaccinated, all patients will receive vaccination against *Neisseria meningitidis*, *Streptococcus pneumoniae*, and *Hemophilus influenzae* within the screening window according to local regulation and practice. All required vaccinations should be done at least 30 days prior to start of treatment. If there is doubt about the success of vaccination, antibody titers can be measured according to local practice. The run-in period may be extended to allow vaccination procedures to be completed before first dose.

Patients who meet the eligibility criteria at screening and following the run-in period will be admitted to the study site on Day -7 /-4 for baseline evaluations (please refer to [Assessment schedule, Table 8-1](#) and [Table 8-2](#)).

All baseline safety evaluation results must be available prior to dosing.

Drug administration and treatment period will start on Day 1.

Safety assessments during the treatment period include for each visit

- Blood pressure
- Infection surveillance
- Hematology and serum chemistry
- Urine chemistry and urinary microscopy
- Physical examination

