- T3, T4, TSH, reversed T3, FSH, LH, testosterone and DHT
- Vital signs
- 12-lead ECG (PR interval, QRS duration, heart rate, RR, QT, QTcF)
- AEs

Efficacy (proteinuria; renal function), PK, [REDACTED] will also be conducted through the study.

[figure not shown]
Patients should return to the site on a regular basis for follow up assessments and approximately 90 days after last dosing for study completion evaluations (EOS).

Design of Part 1:

Approximately forty-eight patients will be enrolled in Part 1 to allow for 40 patients to complete this part of the study. These patients will be randomized to treatment groups as follows: 14 to placebo, 10 to LNP023 10 mg, 10 to LNP023 50 mg and 14 to LNP023 200 mg, all b.i.d.

Study duration for patients enrolled in Part 1 will be of approx. 270 days.

Figure 3-1 Part 1

Design of Part 2:

An interim analysis will be performed when approximately 48 patients have been randomized in Part 1 and have completed treatment to Day 90 (or withdrawn from the trial), as described in the interim analysis section ([Section 3.5](#)).

The design and doses tested for Part 2 will be determined according to pre-specified rules that will be defined in full in the Data Monitoring Committee (DMC) charter. First, a sample size re-estimation will be performed to determine the number of patients to be randomized in Part 2 and secondly, a decision will be made on which dose (either 25 mg or 100 mg b.i.d) is to be added in Part 2. The sample size for Part 2 will be chosen to be in the range of 48 to 100 patients (i.e. to aim for 40 – 85 patients completing the 90 day treatment period in Part 2 of the study). Patients who are enrolled in Part 2, either in screening or run-in phase will not receive blinded study treatment until the interim analysis on Part 1 is completed and DMC recommends to proceed to Part 2 of the study. As a result of available data from interim analysis Part 1 (IA1) of the trial, part 2 of the study will recruit approximately 50 randomized patients.

[figure not shown]
The selection of doses to be used in Part 2 will be guided by the results seen in Part 1. Two scenarios will be considered:

1. placebo, 10 mg, 50 mg, 100 mg and 200 mg b.i.d.
2. placebo, 10 mg, 25 mg, 50 mg and 200 mg b.i.d.

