The selection of doses to be used in Part 2 will be guided by the results seen in Part 1 and a similar study design as for Part 1 will be also employed for Part 2 (Figure 1-2).

Two scenarios will be considered:

Scenario 1: placebo, 10mg, 50mg, 100mg and 200mg b.i.d.

[figure not shown]
Scenario 2: placebo, 10mg, 25mg, 50mg and 200mg b.i.d.

- Scenario 1, using an additional 100mg dose, was chosen by the DMC after IA1.

LNP023 or matching placebo will be administered twice daily for 180 days in a blinded manner. Study duration for patients enrolled in Part 2 will be approximately 360 days.

Patients in Part 2 will be allocated across the five treatment groups. The randomization ratio will be chosen to aim for an approximately equal allocation of patients to treatment groups across the whole study (Parts 1 and 2 combined).

Figure 1-2: Study Design for Part 2

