In addition, 95% confidence intervals will be presented for the occurrence rate. It will be assumed that for each of n subjects the time t_j ($j=1, \dots, n$) represents the duration of exposure to study treatment. The sequence of occurrences of an event will be modeled to follow approximately a Poisson process with constant intensity θ . The rate parameter θ will be estimated as $\lambda = D/T$, where $T = \sum_{j=1}^n t_j$ and D is the total number of events. Conditionally on T , an exact $100 \times (1-\alpha)\%$ confidence interval for a Poisson variable with parameter θT and observed value D can be obtained based on (Garwood, 1936), from which an exact $100 \times (1-\alpha)\%$ confidence interval for $100 \times D/T$ will be derived as follows (Sahai, 1993):

Lower confidence limit $L = \frac{0.5c_{\alpha/2, 2D}}{T} * 100$ for $D > 0$, 0 otherwise,

Upper confidence limit $U = \frac{0.5c_{1-\alpha/2, 2D+2}}{T} * 100$ for $D > 0$, 0 otherwise,

where $c_{\alpha, k}$ is the α th quantile of the Chi-square distribution with k degrees of freedom.

Adverse events of special interest definitions are found in the compound electronic Case Retrieval Strategy (eCRS). The classification reflects the current version of the Development Safety Profiling Plan (DSPP) and might be updated based on review of accumulating data. A listing of the case retrieval strategy will be presented.

The frequency and percentage of patients with adverse events of special interest will be presented by MedDRA preferred term and treatment arm. These outputs will also be produced for the SAF (up to Day 90) and for SAF1 and SAF2 separately.

Further displays of AEs may be produced in order to appropriately describe the outcomes seen in this trial. For displays of Treatment Emergent events only, events will be considered as Treatment emergent if they started after the date of first administration of study treatment (or were present prior to start of study treatment but increased in severity based on preferred term) and up to 7 days after study treatment discontinuation. For post-treatment period, AEs and SAEs will be summarized separately for both SAF1 and SAF2 analysis sets.

For TEAE tables on SAF (Part 1 and Part 2 to Day 90) a cut-off of 90 + 7 days (post end of treatment) for Part 1 patients and Part 2 patients on 90 days of treatment will be used, whereas a cut-off of 90 days for Part 2 patients on 180 days of treatment will be used.

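### The pooled Day-90 TEAE tables count events to Day 97 for 90-day patients but to Day 90 for 180-day patients, so the event window differs slightly by arm

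*SAP*

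**What the plan says.** SAP 8.2 (Adverse events) defines an event as treatment-emergent if it starts after first dose "and up to 7 days after study treatment discontinuation". For the TEAE tables on the safety set pooled over both parts to Day 90, it then applies "a cut-off of 90 + 7 days (post end of treatment) for Part 1 patients and Part 2 patients on 90 days of treatment", whereas "a cut-off of 90 days for Part 2 patients on 180 days of treatment will be used". The AE tables give the number and percentage of subjects by treatment, without adjustment for time.

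Three design features decide who falls under which cut-off:

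- Part 1 was randomized "14 to placebo, 10 to LNP023 10 mg, 10 to LNP023 50 mg and 14 to LNP023 200 mg" (Protocol 3.1), all for 90 days.
- The fourth active dose came later: "Scenario 1, using an additional 100mg dose, was chosen by the DMC after IA1" (SAP 1.4). The 100 mg arm therefore has no Part 1 patients.
- On Part 2 size, Protocol 3.1 says "part 2 of the study will recruit approximately 50 randomized patients". SAP 1.4 sets the Part 2 ratio so that arm totals over both parts come out about equal.

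SAP 5 also provides for Part 2 patients who consented under protocol version 03 or earlier and so have 90 days of treatment. Their number is not given.

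**The concern.** The tables are labelled as running to Day 90 (Protocol 11.5.2, SAP 2), yet for some patients they hold events to Day 97. If both kinds of patient were spread evenly over the arms, this would be only a labelling matter. They are not: most placebo and 200 mg patients come from Part 1, about half of the 10 and 50 mg patients do, and no 100 mg patient does. A crude percentage then gives the arms unequal time in which to record an event, and randomization within each part does not balance that out.

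The additional days also differ in kind. For a patient who completes 90 days they fall after the last dose. A 180-day patient is still on drug on those days, and they are not counted.

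The exposure-adjusted summaries do not repair this. Their denominator in SAP 8.2 is days on drug, which leaves out the seven post-treatment days. What is at stake is a tilt in one descriptive safety table, in a trial meant to inform dose selection.

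**Working it through.** **Inputs.** Windows of 97 (= 90 + 7) and 90 days from SAP 8.2. Part 1 allocation 14/10/10/14 from Protocol 3.1, which sums to the stated 48. Part 2 size about 50 from Protocol 3.1. Equal arm totals from SAP 1.4, so (48 + 50)/5 = 98/5 = 19.6 per arm.

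**Assumptions.** Exactly equal totals, no early discontinuation, and at first every Part 2 patient on 180 days.

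**Average window per arm** = (97 × n on 90 days + 90 × n on 180 days)/19.6.

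| Arm | Part 1 | Part 2 | Share at 97 days | Average window |
|---|---|---|---|---|
| Placebo, 200 mg | 14 | 5.6 | 71% | (14×97 + 5.6×90)/19.6 = 95.0 |
| 10 mg, 50 mg | 10 | 9.6 | 51% | (10×97 + 9.6×90)/19.6 = 93.6 |
| 100 mg | 0 | 19.6 | 0% | 90.0 |

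The placebo to 100 mg ratio is 95.0/90.0 = 1.056.

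**Sensitivity to the unknown number of Part 2 patients on 90 days** (same share in each arm):

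- 25%: placebo 90 + 7×(14 + 1.4)/19.6 = 95.5; 100 mg 90 + 7×0.25 = 91.75; ratio 1.041.
- 50%: placebo 96.0; 100 mg 93.5; ratio 1.027.
- 100%: 97.0 in every arm; ratio 1.00.

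If Part 2 were instead split 10 per arm, with all on 180 days, placebo would average (14×97 + 10×90)/24 = 94.1 days and the ratio would be 1.045.

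**Effect on the crude percentage.** Let every arm have the same constant hazard and an assumed 90-day incidence p. A 97-day patient then has incidence 1 − (1 − p)^(97/90). With p = 30% this is 31.9%, and the placebo arm shows 0.714×31.9% + 0.286×30% = 31.4%, against 30.0% for 100 mg.

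| Assumed 90-day incidence | 100 mg shows | Placebo or 200 mg shows | Difference (points) |
|---|---|---|---|
| 10% | 10.0% | 10.5% | 0.5 |
| 30% | 30.0% | 31.4% | 1.4 |
| 50% | 50.0% | 51.9% | 1.9 |
| 70% | 70.0% | 71.9% | 1.9 |

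At 30% the artefact is 1.37 points × 19.6 patients = about 0.27 of a patient. With about 20 per arm, the standard error of a difference between two arms is √(2×0.3×0.7/20) = 14.5 points, so the artefact is about 0.09 standard errors.

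**After the change.** With one common cap at Day 90, every arm has a 90-day window and the ratio is 1.00.

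**The case against.** The best defence is that the rule looks deliberate. It applies the general seven-day definition to two treatment durations: a 90-day completer has a post-treatment tail to add, while a 180-day patient on Days 91 to 97 is still on drug and has none. Planned on-drug time in the table is 90 days for everyone. This explains where the rule comes from, but it does not make the windows equal.

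The defence is right on several other matters. The effect is a fraction of one patient per arm, and safety is reported descriptively, with no test or threshold attached to this table. AE tables are also planned for SAF1 and SAF2 separately. SAF2 has one planned duration and one rule, so it compares 100 mg with concurrently randomized placebo and the other doses over matched windows. SAP 2 lists that table beside the pooled one among the first interpretable results.

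Two stronger readings are tempting and should be resisted. A reader might infer that the trial's main safety comparison is seriously biased towards 100 mg. The documents nowhere rank the pooled table above the SAF2 table, and the size found does not amount to serious bias. A reader might also infer that events after stopping are counted only for 90-day patients. That is not strictly so: a 180-day patient who stops before Day 90 still contributes post-stop events under the seven-day rule, up to Day 90, and SAP 8.2 plans separate post-treatment summaries for SAF1 and SAF2.

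**Conclusion.** The inconsistency is real and linked to arm, but minor. As written, the pooled Day-90 TEAE tables give placebo and 200 mg a window up to 5.6% longer than 100 mg. That is worth under 2 percentage points of crude incidence across the assumed range, in a direction that slightly flatters 100 mg. Placebo and 200 mg have the same expected mix, as do 10 and 50 mg, so those two comparisons are unaffected.

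The figures rest on 98 patients, equal arm totals, no early discontinuation and a constant hazard. The 5.6% also needs all Part 2 patients to be on 180 days, and it shrinks as that share falls. Protocol 11.7 allows for drop-out of up to 20%, and for early stoppers the 97-day limit often does not apply. Events triggered by stopping would break the constant-hazard assumption, but the documents give nothing from which to size that.

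**What to change.** In SAP 8.2, replace the two cut-offs for the pooled Day-90 TEAE tables with one rule for every patient: count events up to the earlier of Day 90 and 7 days after treatment discontinuation. This keeps the tail after early discontinuation, within Day 90, and matches the table's label. Keep the full seven-day tail in the SAF1 and SAF2 tables, where the general definition already puts it. Extending everyone to Day 97 would also equalise the length, but it would mix off-treatment days in one group with on-treatment days in the other.

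The cost is one SAP sentence and one programming condition. SAP 8 already plans to rerun the safety analyses after database lock. The downside is that events on Days 91 to 97 in 90-day patients would appear only in the SAF1 table. That includes any on-drug events when the Day 90 visit falls late in its ±3-day window. A footnote to the pooled tables should say so.

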3.1 Study design

This is a multicentre, randomized, double blinded (investigator, subject and sponsor blinded), placebo-controlled, dose-ranging, parallel-group adaptive design.

The study comprises a run-in phase of at least 30 days, a 90 days treatment phase in Part 1; a 180 days treatment phase in Part 2 and a 90 days follow-up phase in both Parts 1 and 2.

At screening, patients must have UPCr ≥ 0.8 g/g (≥ 90 mg/mmol) sampled from first morning void (FMV) or urine protein ≥ 0.75 g/24hr from a 24h urine collection. Patients will remain on their supportive therapy, i.e. ACEi or ARB with or without diuretics, statins or antihypertensive therapy for the duration of the trial. Patients who complete the Run-in Phase with a 24-hr urine protein excretion of ≥ 0.75 g/24hr will be eligible for randomization and entry into the Treatment Phase of the trial. To be dosed, patients must have been on stable therapy with an ACEi or ARB for at least 90 days at the maximally tolerated dose (KDIGO 2012, see Section 4.2 Exclusion criteria below). If dose adjustments of ACEi/ARB, or diuretics are required, the Run-in Phase needs to be extended to ensure stable ACEi/ARB and diuretic medication. Run-in phase can be extended to minimize patient risk of visit sites during the COVID-19 pandemic. During the Treatment Phase, no change in these medications is allowed except for safety reasons.

Patients enrolled into Part 1 of the study will initially be randomized to one of four treatment arms and treated for 90 days with placebo, or active therapy with LNP023 at doses of: 10 mg, 50 mg or 200 mg twice daily (b.i.d.).

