3.5 Purpose and timing of interim analyses/design adaptations

An interim analysis will be performed when approximately 48 patients have been randomized in Part 1 and have completed treatment to Day 90 (or withdrawn from the trial). The intention of this analysis is to provide preliminary evidence of dose-response relationship for proteinuria, to determine the sample size for Part 2, and to determine the additional treatment arm of either 25 mg or 100 mg b.i.d to be studied in Part 2.

[figure not shown]
Three decision steps will follow from this interim analysis:

- Step 1 Assess futility: Data from Part 1 will be analyzed using the MCP-Mod procedure [Bretz et al 2005](#). If the maximum observed effect (i.e. the maximum of the point estimates from the analysis) is not greater than a 20% reduction in UPCR, or the one-sided p-value for the multiple contrast test is ≥ 0.1 then do not continue to Part 2.
- Step 2 Sample size re-estimation for Part 2: The total sample size will be calculated which provides sufficient information for primary analysis (see [Section 11.9](#)).
- Step 3 Select doses to be studied in Part 2. The Mod step (from MCP-Mod) will determine which of the candidate models (as described in [Section 11.4.2](#)) is likely to represent the best fit to the data. Based on this, [Figure 3-3](#) provides the general decision rule for recommendation of dose selection for Part 2 of the trial.

However the DMC will additionally take into consideration all the efficacy and safety data assessed at the IA for their recommendations.

As a result of available data from interim analysis Part 1 (IA1) of the trial, part 2 of the study will recruit approximately 50 randomized patients. Based on IA1 results, an additional 100 mg dose was chosen by the DMC to be added into Part 2.

Figure 3-3 Dose selection guideline based on primary endpoint

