Clinical laboratory evaluations

All laboratory data will be listed by treatment, subject, and visit/time and if normal ranges are available abnormalities will be flagged. A separate listing will be provided presenting all parameters in a subject with any abnormal values. Summary statistics will be provided by treatment and visit/time, for the SAF (up to Day 90) and for SAF1 and SAF2 separately. Summary statistics will include mean, SD, CV, Q1, median, Q3, minimum and maximum as appropriate. Values less than the Lower Limit (LL) will be imputed as $0.5 \times LL$ and values greater than the Upper Limit (UL) will be imputed as $1.5 \times UL$. The number and percentage of values below the LL and above the UL will be presented. For the figures, imputed values will be displayed.

Adverse events

All information obtained on adverse events will be displayed by treatment and subject. All information obtained on deaths will be likewise provided.

The overall incidence of treatment emergent AEs will be summarized by treatment group for the SAF (up to Day 90), SAF, SAF1 and SAF2 populations separately.

The number and percentage of subjects with adverse events will be tabulated by body system organ class (SOC) and preferred term (PT) with a breakdown by treatment, for the SAF (up to Day 90) and for SAF1 and SAF2 separately. A subject with multiple adverse events within a

body system is only counted once towards the total of this body system and treatment, for the event with highest severity. Summaries of SAEs will be provided in a similar manner.

A summary table of AEs leading to discontinuation of study treatment by preferred term will be produced for the SAF (up to Day 90), SAF1 and SAF2 separately.

Exposure-adjusted AE summaries will also be likewise considered for SAF.

For summary tables on exposure-adjusted AEs, the number of episodes per 100 patient months will be presented. The occurrence rate (number of episodes per 100 patient month) will be calculated as $100 \times (\text{the total number of AE episodes from all patients in the population divided by the total number of patient-months})$. A patient may have multiple occurrences of the same event. All occurrences are counted. Total patient months will be computed as $(\text{sum of the duration of exposure over patients, in days})/30.4375$. This method will account for the length of follow-up time under the assumption that events would occur with the same frequency at any point in time.

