For the legal requirements of ClinicalTrials.gov and EudraCT, two required Safety disclosure tables on treatment emergent adverse events which are not serious adverse events with an incidence greater than a certain threshold based on the final database and on treatment emergent serious adverse events and SAE suspected to be related to study treatment will be provided by system organ class and preferred term on the safety set population.

If for a same patient, several consecutive AEs (irrespective of study treatment causality, seriousness and severity) occurred with the same SOC and PT:

- a single occurrence will be counted if there is ≤ 1 day gap between the end date of the preceding AE and the start date of the consecutive AE
- more than one occurrence will be counted if there is > 1 day gap between the end date of the preceding AE and the start date of the consecutive AE.

For occurrence, the presence of at least one SAE / SAE suspected to be related to study treatment / non SAE has to be checked in a block e.g., among AE's in a ≤ 1 day gap block, if at least one SAE is occurring, then one occurrence is calculated for that SAE.

The number of deaths resulting from SAEs suspected to be related to study treatment and SAEs irrespective of study treatment relationship will be provided by SOC and PT.

Physical Examination

Significant findings prior to informed consent will be recorded in the Medical history eCRF and any significant findings after informed consent will be recorded on the Adverse Events and thus will be summarized respectively.

Protocol deviations

Protocol deviations will be listed by treatment, subject and epoch period. A frequency summary table will be produced by treatment period for all protocol deviations (including Covid related).

Others

All pregnancy data will be listed by treatment, subject, and visit/time.

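### Crude TEAE incidence on the uncut safety set, and probably the registry disclosure tables, compares arms whose planned time at risk differs by design, which favours placebo and 200 mg over 100 mg

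*SAP*

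**What the plan says.** **Duration and allocation.** Protocol 3.1 plans "a 90 days treatment phase in Part 1; a 180 days treatment phase in Part 2". Part 1 randomises "14 to placebo, 10 to LNP023 10 mg, 10 to LNP023 50 mg and 14 to LNP023 200 mg". Protocol 3.5 records that "an additional 100 mg dose was chosen by the DMC to be added into Part 2", and Protocol 3.1 that "part 2 of the study will recruit approximately 50 randomized patients". SAP 1.4 adds: "The randomization ratio will be chosen to aim for an approximately equal allocation of patients to treatment groups across the whole study".

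**TEAE window.** SAP 8.2 counts events from first dose "up to 7 days after study treatment discontinuation", so the window follows each patient's own treatment period.

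**Tables.** SAP 8.2 has overall TEAE incidence "summarized by treatment group for the SAF (up to Day 90), SAF, SAF1 and SAF2 populations separately". The plain SAF stands beside its Day 90 version, so it is uncut. The two ClinicalTrials.gov/EudraCT tables cover non-serious TEAEs above an incidence threshold, and treatment-emergent and related SAEs. They "will be provided by system organ class and preferred term on the safety set population", from the final database. No cut, split by duration or exposure adjustment is stated for them.

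**Elsewhere in SAP 8.2.** The tables by SOC and PT, and those for SAEs, discontinuations and events of special interest, are given for SAF to Day 90, SAF1 and SAF2. An exposure-adjusted AE summary is planned on the SAF.

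**The concern.** The percentage of patients with at least one event rises with time at risk. Every 100 mg patient comes from the part with 180 days of treatment, whereas most placebo and 200 mg patients come from the part with 90 days. Pooled in one column per arm, equal true risk then gives unequal expected percentages, with 100 mg highest. A reader of a public registry sees what looks like a non-monotone dose pattern in harms, 100 mg above 200 mg, without the exposure information needed to discount it. Safety and tolerability is a stated secondary objective of this dose-ranging trial, so the harm columns should be comparable across doses wherever they are published.

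**Working it through.** **Inputs from the documents.** Part 1 numbers are 14, 10, 10 and 14 for placebo, 10, 50 and 200 mg (sum 48). Part 2 is about 50. The total of 98 agrees with the approximately 100 patients in the protocol's Amendment 5 rationale. The TEAE window is 90 + 7 = 97 days or 180 + 7 = 187 days.

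**Assumptions.** Equal arms overall, 98/5 = 19.6 each; all Part 2 patients on 180 days; no dropout; the same constant event rate in every arm. The documents give no event rates, so a range of 97-day risks *p* is used.

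**Step 1: planned window by arm.** Part 2 number = 19.6 − Part 1 number. Mean window = (n1 × 97 + n2 × 187)/19.6.

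| Arm | n1 (90 days) | n2 (180 days) | Share on 180 days | Mean window (days) |
|---|---|---|---|---|
| Placebo, 200 mg (each) | 14 | 5.6 | 29% | 122.7 |
| 10 mg, 50 mg (each) | 10 | 9.6 | 49% | 141.1 |
| 100 mg | 0 | 19.6 | 100% | 187.0 |

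**Step 2: expected crude incidence under equal risk.** Risk over 187 days = 1 − (1 − p)^(187/97). Arm incidence = (n1 × p + n2 × 187-day risk)/19.6.

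For p = 20%, the 187-day risk is 1 − 0.8^1.928 = 35.0%. Placebo and 200 mg: (14 × 0.20 + 5.6 × 0.350)/19.6 = 24.3%. The 10 and 50 mg arms: 27.3%.

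| 97-day risk | Placebo or 200 mg | 100 mg | Ratio |
|---|---|---|---|
| 5% | 6.3% | 9.4% | 1.50 |
| 10% | 12.4% | 18.4% | 1.48 |
| 20% | 24.3% | 35.0% | 1.44 |
| 40% | 46.5% | 62.6% | 1.35 |
| 60% | 66.5% | 82.9% | 1.25 |

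**Step 3: sensitivity at the 20% risk.**
- 20% dropout per 90 days: 21.2% v 28.9%, ratio 1.36.
- Front-loaded events (Weibull shape 0.5): 21.9% v 26.6%, ratio 1.22.
- 25% of Part 2 on 90 days: 23.2% v 31.2%, ratio 1.35.
- 50% of Part 2 on 90 days: 22.1% v 27.5%, ratio 1.24.
- All of Part 2 on 90 days: no gap.

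**Step 4: chance variation.** Take 20 patients per arm, with placebo as 14 short and 6 long. The exact probability under equal risk that 100 mg shows a higher percentage than placebo is 62%, 71%, 81% and 85% at 97-day risks of 10%, 20%, 40% and 60%. The reverse order occurs in 23%, 18%, 12% and 8%; the rest are ties. With a common window, 100 mg is higher in 39% to 44%.

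**Step 5: the SAP's other displays.**
- Day 90 tables (97 days for 90-day patients, 90 days for 180-day patients), at the 20% risk: placebo 19.6%, 100 mg 18.7%. The gap is nearly gone and slightly reversed.
- Exposure-adjusted rate, with events over T + 7 days divided by T days: placebo (14 × 97 + 5.6 × 187)/(14 × 90 + 5.6 × 180) = 2405.2/2268 = 1.061; 100 mg 187/180 = 1.039. The ratio under equal risk is 0.98.

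**The case against.** The strongest reply is that this is narrow and largely handled. Much of that stands.

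- **Layout.** The disclosure paragraph does not mention treatment columns or percentages by arm; the table shells are a separate document. Only the uncut SAF summary is expressly by treatment group. Columns by arm are still the natural reading of incidence in a randomised trial, and nothing rules out pooling the two durations.
- **Mitigation.** The uncut SAF row has three duration-controlled versions beside it, and an exposure-adjusted SAF table is planned. That helps the uncut summary. The adjusted table counts episodes rather than patients, however, and nothing links it to the disclosure tables.
- **Dose selection.** A reader might infer that dose choice would be distorted. The documents do not support this. SAP 8.2 ties the disclosure tables to registry requirements; Protocol 6.4 says IA1 and IA2 support starting phase 3, and SAP 3 lists the IA2 outputs separately.
- **Certainty.** A reader might infer that 100 mg will look worse. Step 4 shows only a shift in expectation. For a single 5% term, the gap is about 3.1 points on 19.6 patients, or 0.6 of a patient.
- **Threshold.** A reader might infer that terms will pass the incidence threshold only because of the longer window. The SAP gives neither its value nor whether it applies per arm, so this cannot be shown.
- **Number on 90 days.** SAP 5 provides for Part 2 patients on 90 days but gives no count, so the full-size figures are an upper case on that point.

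**Conclusion.** The point holds for the uncut SAF incidence by arm as written, and for the disclosure tables if their columns are arms. Under equal true risk, the expected crude incidence at 100 mg exceeds that at placebo and 200 mg, by a ratio of about 1.25 to 1.5 over 97-day risks of 5% to 60%. The 10 and 50 mg arms lie between. These figures rest on equal overall allocation, a constant rate, no dropout and all Part 2 patients on 180 days. At the 20% risk, relaxing the last three one at a time leaves a ratio of about 1.2 to 1.4, unless all of Part 2 had 90 days.

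The main AE tables are not affected beyond the small 97- against 90-day difference. A reader might infer a general flaw in the safety analysis; the existing split into SAF to Day 90, SAF1 and SAF2 shows otherwise. The change is worth making because it is cheap and these are the tables meant for public registries.

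**What to change.** In SAP 8.2:

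1. Give the two disclosure tables, and the related-SAE and death counts, with treatment columns split by planned duration, using the existing SAF1 (90 days) and SAF2 (180 days). As defined in SAP 5, the two sets together hold every treated patient, so no event is lost.
2. Apply the incidence threshold to the total of each set, not per arm. In SAF2 about 6 patients would be on placebo and about 6 on 200 mg. One event there is about 17% (1/6), against 5% (1/20) at 100 mg, so a per-arm rule would let single events pass.
3. Drop the uncut-SAF incidence by arm, or show it only as a total, with exposure per arm and a pointer to the exposure-adjusted rates.

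**Cost.** A short SAP amendment and a column split in existing programs. The downside is more columns and small SAF2 denominators (about 5 to 6 patients on placebo and on 200 mg), which the SAP already accepts in its other SAF2 tables.
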